#### LIST OF ABBREVIATIONS AND RELEVANT DEFINITIONS

ABR ABR form, General Assessment and Registration form, is the application form that is

required for submission to the accredited Ethics Committee (In Dutch, ABR = Algemene

Beoordeling en Registratie)

AE Adverse Event

AR Adverse Reaction

**CA** Competent Authority

**CCMO** Central Committee on Research Involving Human Subjects; in Dutch: Centrale Commissie

Mensgebonden Onderzoek

**CRC** Colorectal cancer

**CV** Curriculum Vitae

**DSMB** Data Safety Monitoring Board

**EKG** Electrocardiography

**EU** European Union

**EudraCT** European drug regulatory affairs Clinical Trials

**FAP** Familial adenomatous polyposis

**GCP** Good Clinical Practice

**HRQoL** Health related quality of life

**IB** Investigator's Brochure

IC Informed Consent

IMP Investigational Medicinal Product

**IMPD** Investigational Medicinal Product Dossier

**IPAA** Ileo-anal pouch anastomosis

IRA Ileo-rectal anastomosis

**LGI** Lower gastrointestinal

METC Medical research ethics committee (MREC); in Dutch: medisch ethische toetsing

commissie (METC)

(S)AE (Serious) Adverse Event

**SPC** Summary of Product Characteristics (in Dutch: officiële productinfomatie IB1-tekst)

**Sponsor** The sponsor is the party that commissions the organisation or performance of the

research, for example a pharmaceutical company, academic hospital, scientific

organisation or investigator. A party that provides funding for a study but does not

commission it is not regarded as the sponsor, but referred to as a subsidising party.

Version number: ,date 6 of 40

**SUSAR** Suspected Unexpected Serious Adverse Reaction

**ULN** Upper limit of normal

**Wbp** Personal Data Protection Act (in Dutch: Wet Bescherming Persoonsgevens)

**WMO** Medical Research Involving Human Subjects Act (in Dutch: Wet Medisch-wetenschappelijk

Onderzoek met Mensen

Version number: ,date 7 of 40

#### **SUMMARY**

Rationale: Due to the presence of numerous colorectal polyps, nearly all patients with familial adenomatous polyposis (FAP) develop colorectal cancer (CRC) at an average age of 45 years, if left untreated. Therefore, a prophylactic colectomy is recommended. After surgery, adenomas are likely to reappear in the pouch or rectum. Recently, studies in APC-deficient mice have shown that the mTOR inhibitor sirolimus can cause intestinal tumour cells to undergo growth arrest and differentiation and could even lead to regression of polyps. In current practice, sirolimus is used as an immunomodulator for patients after renal transplantation. Sirolimus has never been investigated in patients with FAP. We hypothesize that sirolimus could lead to regression of intestinal polyps in patients with FAP.

**Objective**: The aim of our study is to investigate the effect of sirolimus on the progression of intestinal adenomas in patients with FAP and to assess the safety of this treatment.

**Study design:** A prospective phase II pilot study with a follow-up of 6 months.

**Study population:** Five patients with FAP will be selected and invited for study participation. They need to be 18 years or older, have a genetically confirmed APC mutation with a classical FAP phenotype and a subtotal colectomy with an ileo-rectal anastomosis (IRA) or a total colectomy with an ileo-anal pouch anastomosis (IPAA) with severe polyposis.

**Intervention**: All patients will receive sirolimus for the duration of the study, with a trough level target range of 5-8 ng/ml.

Main study parameters/endpoints: The main study parameters are the effect of sirolimus on the size of 5 marked polyps and safety of this treatment. Safety outcomes will be assessed by summary analysis of adverse events, clinical laboratory abnormalities and regular physical examination.

Additional parameters are the effect on the number of polyps, global polyp burden, histopathology and patient-reported quality of life. Cell proliferation and immunohistochemistry of mTOR targets in healthy intestinal mucosa and adenomatous tissue will be assessed.

Nature and extent of the burden and risks associated with participation, benefit and group relatedness: At baseline and at three monthly visits a medical history will be taken and physical examinations will be performed, as well as laboratory tests and HRQoL questionnaires. Trough level testing of sirolimus will be measured at day 7 after start of the study drug and weekly until the therapeutic range has been achieved, after which the next trough level will be measured at 3 and 6 months follow-up. Finally, monthly telephone check-ups will be carried out. LGI endoscopies will be done at baseline and at 6 months. For this study, we include patients with severe rectal or pouch polyposis as they are expected to have an indication for invasive surgery on a short-term base and no other less invasive alternative therapy is available.

#### 1. INTRODUCTION AND RATIONALE

Familial adenomatous polyposis (FAP) is a syndrome caused by mutations in the adenomatous polyposis coli (APC) tumor suppressor gene. It follows an autosomal dominant pattern of inheritance and up to 25% of all cases are due to *de novo* mutations (1). This syndrome is characterized by the presence of numerous colorectal adenomas, usually more than hundred, from a young age (2). If left untreated, colorectal cancer (CRC) develops in nearly 100% of all patients with a mean age at diagnosis of 45 years (3). Therefore, international guidelines recommend a prophylactic colectomy for these patients (4-7). After surgery, surveillance sigmoidoscopies are needed as adenomas are likely to reappear in the pouch or rectum (8, 9). In addition to colorectal adenomas, patients with FAP usually develop duodenal adenomas as well as extraintestinal manifestations, such as desmoid tumors and fundic gland polyps (10-12).

In recent years several drug therapies have been investigated that aimed to decrease the number and size of polyps in patients with FAP, with none of them providing sufficient evidence of success (13). However, recently studies in APC-deficient mice demonstrated that mTOR inhibitor sirolimus can cause intestinal tumour cells to undergo growth arrest and differentiation (14). Signalling through the mTOR pathway is required for epithelial cell proliferation and tumour growth (15, 16). It was shown that mTOR complex 1 (mTORC1) activity is required for the proliferation of APC-deficient enterocytes. This complex mediates inhibition of eEF2 kinase, which is needed for the proliferation of APC-deficient cells. Sirolimus targets eEF2 resulting in growth arrest and differentiation of tumour cells. The effect of sirolimus on colonic adenoma regression was confirmed in other mice studies, with one of them showing beneficial effects in the small bowel (17-22). Sirolimus seems to inhibit polyp formation and could even lead to regression of polyps (21, 23). Moreover, it seems to increase survival and time to progression to dysplasia (20, 21).

Sirolimus has been widely investigated in human studies. It received FDA approval in 1999 as immunosuppressive agent for the treatment of patients with renal transplantations. Data on toxicity, contra-indications, interactions and dosing advice are available and based on data collected in patients with renal transplantations (24). Some of the most frequently (>10%) occurring side-effects are thrombocytopenia and anemia, hypertension, electrolyte disorders, urinary tract infections, hypercholesterolemia, hyperglycemia and abdominal pain. Less frequent, but more severe side-effects are sepsis, deep venous thrombosis and skin cancer (Table 1).

Version number: ,date 9 of 40

This drug has not yet been evaluated in patients with FAP. In this pilot study (phase II), the possible polyp reducing effect of sirolimus will be investigated in a small number of patients with FAP, who suffer from severe intestinal polyposis. Patients who are expected to undergo rectal or pouch-related surgery on a short- term base (to avoid the development of cancer), will be selected and invited for study participation. Both rectal and pouch surgery are invasive and associated with a significant morbidity and mortality and neither does it prevent the development of adenomas in the remaining intestinal tissue as previously described. Therefore these patients could potentially benefit from a new and less invasive FAP related drug therapy to postpone, or eventually even prevent, surgery.

The aim of our study is to investigate the effect of sirolimus on the progression of intestinal adenomas in patients with FAP and to assess the safety of this treatment.

Version number: ,date 10 of 40

#### 2. OBJECTIVES

## **Primary objective:**

- To evaluate the effect of sirolimus on the size of 5 marked polyps in 5 patients with FAP and a large intestinal polyp burden
- To assess safety outcomes by summary analysis of adverse events, clinical laboratory abnormalities and regular physical examination.

## **Secondary Objectives:**

- To evaluate the effect on number of polyps
- To evaluate the effect on global polyp burden (see definition in chapter 7.2)
- To evaluate the effect on histology (tubular, tubulovillous or villous histology and degree of dysplasia)
- To evaluate patient reported quality of life using health related quality of life (HRQoL) questionnaires (EORTC QLQ-C30, SF-36, CR29 and EQ-5D-5L)
- To measure the rate of cell proliferation in healthy intestinal mucosa and adenomatous tissue
- To assess immunohistochemistry of mTOR targets (such as eEF2 kinase, phospho-S6) in healthy intestinal mucosa and adenomatous tissue

Version number: ,date 11 of 40

#### 3. STUDY DESIGN

This is a prospective phase II pilot study that will take place at the Academic Medical Center (AMC). Five patients with FAP will be invited for study participation. The total study duration will be 6 months. At baseline and at 6 months follow-up all included patients will undergo a lower gastrointestinal (LGI) endoscopy. Safety outcomes will be assessed by laboratory tests, physical examinations and telephone check-ups. Sirolimus trough levels will be measured regularly and if needed dosing adjustments will be made.

#### **Baseline**

- · Medical history & physical examination (including vital signs)
- · Laboratory tests (hematology¹, chemistry², pregnancy test, urine specimen)
- · HRQoL questionnaires
- · LGI endoscopy
- · Day 7: Trough level testing of sirolimus on day 7 after start study drug and weekly until the therapeutic range has been achieved

#### Month 1 & 2

· Monthly telephone check-ups to assess the occurrence of (non-)serious adverse events

## Month 3

- · Monthly telephone check-ups to assess the occurrence of (non-)serious adverse events
- · Medical history & physical examination (including vital signs)
- · Laboratory tests (hematology, chemistry, pregnancy test, urine specimen)
- · HRQoL questionnaires
- $\cdot \textit{Trough level testing of sirolimus and weekly until the the rapeutic range has been achieved} \\$

## Month 4 & 5

· Monthly telephone check-ups to assess the occurrence of (non-)serious adverse events

#### IJ

#### Month 6

- · Monthly telephone check-ups to assess the occurrence of (non-)serious adverse events
- · Medical history & physical examination (including vital signs)
- · Laboratory tests (hematology¹, chemistry², pregnancy test, urine specimen)
- · HRQoL questionnaires
- · LGI endoscopy
- · Trough level testing of sirolimus

#### Month 7

- . Additional telephone check-up to assess the occurrence of (non-)serious adverse events
- 1. Hb, leukocytes, thrombocytes 2. ALAT, ASAT, AF, GGT, AF, LDH, chol, triglyc, potassium, phosphate, creatinine, glucose, calcium, albumin

Version number: ,date 12 of 40

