#### Lab results:

- -Abnormal laboratory results (assessed within 14 days prior to start of study drug):
  - -Significant abnormalities in hepatic function

-ALAT, ASAT, GGT, AF, LDH: > 1.5 times ULN

-Significant hematologic abnormalities

-Hb: <7.0 mmol/L

-Thrombocytes: <100 10E9/L

-Leukocytes: <4.0 10E9/L

-Increased fasting serum cholesterol or triglyceride (whether or not on lipid-lowering therapy)

-Serum cholesterol: >7.8 mmol/L

-Serum triglycerides: >4.5 mmol/L

-Increased glucose (venous, fasting): >6.4 mmol/L

-Electrolyte abnormalities

-Total serum calcium (corrected for albumin): <2.0 mmol/L

-Potassium: <3.0 mmol/L

-Phosphate: <1.3 mmol/L

-Calculated glomerular filtration rate (GFR) less than 40 mL/min/1.73m2 using the simplified Modification of Diet in Renal Disease (MDRD) formula

-Urine specimen:

-Spot urine protein to creatinine ratio (UPr/Cr) greater than or equal to 0.5

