#### 6.4 Summary of known and potential risks and benefits

Please see the SPC text of sirolimus. Some of the most frequently (>10%) occurring side-effects are thrombocytopenia and anemia, hypertension, electrolyte disorders, urinary tract infections,

Version number: ,date 17 of 40

hypercholesterolemia, hyperglycemia and abdominal pain. Some of the less frequent, but more severe side-effects are sepsis, deep venous thrombosis and skin cancer and self-limiting oral stomatitis. All known side-effects can be found in the Table 1. The incidence of several of these side-effects can increase by an increasing trough level of sirolimus. By applying a relatively low dosing range and frequent trough level testing, we believe these risks have been minimized in our study.

Side-effects of sirolimus as reported in the SPC text apply to patients with a renal transplantation. Most of these side-effects were reported in patients who used sirolimus in combination with other immunosuppressive drugs. We exclude patients who use other immunosuppressive therapy. Moreover, compared to patients with FAP, patients with a renal transplantation more frequently have (severe) comorbidities and additionally, sirolimus will be given for a short amount of time (6 months). Therefore, side-effects of sirolimus might be less frequently found in our participants.

We will use tattoos with SPOT™ for marking the polyp sites, which has been used for many years in colonoscopy practice (26). No side-effects of SPOT have been described in literature. Furthermore, colonic biopsies are accompanied by a minimal risk of perforation, bleeding and infection. These complications have been described in some case reports after hot biopsy but mostly in patients with pre-existent ulcerative colitis or infectious colitis. Bleeding after hot biopsy has been reported to occur in up to 0.26% and perforation in up to 0.01% after hot biopsy. During our study only cold biopsies will be obtained. Only case reports have reported on complications after cold biopsy (27, 28). These potential complications are cited in the written patient information.

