As described in chapter 6.2, a significant polyp reducing effect of sirolimus is to be expected. The patients that will be included, are likely to undergo a subtotal colectomy with ileoanal pouch anastomosis or an end ileostomy on a short term base due to the severity of polyposis. These invasive types of surgery are accompanied with a significant risk of comorbidities (29). Even after surgery, patients will develop polyps in the remaining intestinal tissue and therefore surveillance sigmoidoscopies are needed to prevent the development of cancer (5, 30-32). There is currently no alternative treatment available for these patients. Therefore, a medical treatment to postpone or even prevent surgery could be beneficial. If a polyp reducing effect is shown, this therapy could possibly also be beneficial in postponing a preventive colectomy in patients with FAP who have their colon in situ and in postponing a duodenectomy in patients with severe duodenal polyposis.

Version number: ,date 18 of 40

Table 1. Side-effects of sirolimus (SPC)

System/organ	Very frequent	Frequent	Less frequent	Seldom
	(≥1/10)	(≥1/100 to <1/10)	(≥1/1000 to <1/100)	(≥1/10.000 to <
Infections	Pneumonia Fungal infection Viral infection Bacterial infection Herpes simplex infection Urinary tract infection	Sepsis Pyelonephritis CMV infection Herpes zoster infection	Clostridium difficile colitis Mycobacterial infection (incuding tuberculosis) EBV viral infection	
Neoplasms, benign, malignant and non-specified (including cysts and polyps)		Skin cancer	Lymphoma/ post- transplantation lymphoproliferative conditions	
Blood and lymphatic disorders	Thrombocytopenia Anemia Leukopenia	Hemolytic-uremic syndrome Neutropenia	Pancytopenia Thrombotic thrombocytopenic purpura	
Hepatic and biliary disorders			Hepatic failure	
Immune system disorders		Hypersensitivity disorders such as anaphylactic/anaphylactoid reactions, angio-edema		
Feeding and metabolic disorders	Hypokalemia Hypophosphatemia Hyperlipidemia (such as Hypercholesterolemia) Hyperglycemia Hypertriglyceridemia Diabetes mellitus			
Nervous system disorders*	Headache			
Cardiac disorders	Tachycardia	Pericard effusion		
Vascular disorders	Lymphocele Hypertension	Venous thrombosis (such as deep venous thrombosis)	Lymphedema	
Respiratory, chest and mediastinal disorders		Pulmonary embolism Pneumonitis Pleural effusion Epistaxis	Pulmonary hemorrhage	Alveolar protein

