#### 7. METHODS

## 7.1 Study parameters/endpoints

#### 7.1.1. Main study parameter/endpoint

- Size of 5 marked polyps in 5 patients with FAP and a large intestinal polyp burden
- Safety outcomes reported by summary analysis of adverse events, clinical laboratory abnormalities and regular physical examination

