#### 7.2 Study procedures

## Baseline and follow-up measurements and monitoring

- -Medical history and physical examination (including vital signs) at baseline and at three monthly visits
- -Lab testing at baseline and at three monthly visits: pregnancy test, urine specimen, hemoglobin, thrombocytes, cholesterol, triglycerides, glucose, potassium, phosphate, calcium, LDH, ALAT, ASAT, GGT, AF, leukocytes, creatinine, albumin.
- -Three monthly HRQoL questionnaires
- -Trough level testing of sirolimus (using the LC-MS/MS method) on day 7 after start study drug and weekly until the therapeutic range has been achieved, after which the next trough level will be measured at three months
- -Monthly telephone check-ups to assess the occurrence of (non-)serious adverse events

Version number: ,date 22 of 40

-LGI endoscopies at baseline and at six months. Endoscopic procedures will be performed after bowel preparation with sedation according to the standard of care by experienced endoscopists.

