#### 7.3.1 Specific criteria for withdrawal

Participants will be withdrawn from treatment under the following circumstances:
-If any of the exclusion criteria apply during the study

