## 8.4 Follow-up of adverse events

All AEs will be followed until they have abated, or until a stable situation has been reached. Depending on the event, follow up may require additional tests or medical procedures as indicated, and/or referral to the general physician or a medical specialist.

SAEs need to be reported till end of study within the Netherlands, as defined in the protocol.

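### The scheduled haematology panel counts total leukocytes only, so isolated, asymptomatic neutropenia with a total of at least 4.0 x10E9/L would not be detected at the study visits

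*Combined protocol and SAP*

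**What the plan says.** The plan states its blood tests twice. Footnote 1 to the visit schedule in section 3 defines haematology as "Hb, leukocytes, thrombocytes". The list in section 7.2 reads "urine specimen, hemoglobin, thrombocytes, cholesterol, triglycerides, glucose, potassium, phosphate, calcium, LDH, ALAT, ASAT, GGT, AF, leukocytes, creatinine, albumin". Neither asks for a differential or a neutrophil count.

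The main endpoint in section 7.1.1 includes "Safety outcomes reported by summary analysis of adverse events, clinical laboratory abnormalities and regular physical examination".

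Table 1 in section 6.4 puts neutropenia in the frequent column for blood disorders ("Hemolytic-uremic syndrome Neutropenia"), defined as at least 1/100 and below 1/10. Leukopenia is a separate entry in the very frequent column.

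The only white-cell limit is the exclusion criterion in section 4.3, "Leukocytes: <4.0 10E9/L". Section 7.3.1 carries it into the study by withdrawing participants from treatment "If any of the exclusion criteria apply during the study".

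Section 11.2 counts laboratory testing among the measures expected to detect side-effects early.

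**The concern.** Total leukocytes are a sum over cell types. Neutrophils can be low while the sum stays within limits, and the scheduled panel would then record nothing abnormal. By listing leukopenia and neutropenia as separate effects, the plan's own table treats them as different events.

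Section 9 provides descriptive statistics only, so the observed abnormalities are themselves the safety result. Section 11.1 (item i) says that a safe regimen could lead to a later study of a higher dose for a longer period. A laboratory summary without neutropenia could be taken as evidence that it did not occur, when neutrophils had not been counted.

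**Working it through.** The plan gives no sample size, power or event-rate calculation to reproduce. The check compares the lists and then sets a scale.

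**1. Is neutropenia covered by a scheduled test?**

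| Laboratory effect in Table 1 (very frequent or frequent) | Scheduled test (sections 3 and 7.2) |
|---|---|
| Anemia, thrombocytopenia, leukopenia | Hb, thrombocytes, leukocytes |
| Low potassium, low phosphate | potassium, phosphate |
| Raised lipids, raised glucose | cholesterol, triglycerides, glucose |
| Raised LDH, creatinine, liver tests | LDH, creatinine, ALAT, ASAT, GGT, AF |
| Proteinuria | urine specimen |
| Neutropenia | none |

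The panel otherwise follows Table 1 closely, and the plan gives no reason for this gap. Outside Table 1, neutrophils are not mentioned.

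**2. Can the total count stand in?** Neutrophils = total − other white cells. The values below are assumed for illustration and are not from the documents.

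- Total 4.0 x10E9/L (not below the limit), other white cells 2.5, 3.0 or 3.5: neutrophils 1.5, 1.0 or 0.5 x10E9/L.
- Total 4.5 x10E9/L with 20% neutrophils: 4.5 × 0.20 = 0.9 x10E9/L.

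All four cases pass the limit of 4.0. This shows that the total cannot identify neutropenia. It does not show how often such cases occur.

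**3. How likely is any neutropenia in 5 patients?** Inputs: n = 5 (section 4.4) and p from Table 1's frequent band. The calculation assumes that patients are independent and that the band applies here. Expected cases = 5p, and P(at least one) = 1 − (1 − p)^5.

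| p | Expected cases | P(at least one) |
|---|---|---|
| 1% | 0.05 | 1 − 0.99^5 = 4.9% |
| 5% | 0.25 | 1 − 0.95^5 = 22.6% |
| 10% (upper bound, itself excluded) | 0.50 | 1 − 0.90^5 = 41.0% |

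The top of the band is therefore just under 41%, with fewer than 0.5 cases expected.

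**4. What part of this would be missed?** Only cases that (a) leave the total at 4.0 x10E9/L or above and (b) cause no symptom or other recorded event. The documents do not allow that share to be estimated, so the figures in step 3 are a ceiling.

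**5. Number of samples.** 5 patients × 3 scheduled panels = 15, of which 5 × 2 = 10 (months 3 and 6) are on treatment.

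**The case against.** The main safety endpoint is wider than the laboratory panel. Section 8.2.1 records every adverse event that is reported or observed. Section 8.2.2 has subjects questioned at least monthly. Section 8.4 says that "follow up may require additional tests or medical procedures as indicated", and under section 8.5 the safety committee decides what happens next. A low total count or an infection could thus lead to a differential, and a total below 4.0 x10E9/L already triggers withdrawal from treatment. This stands. A reader might infer from the panel that the trial has no means of finding neutropenia at all, and the documents do not support that. These routes do, however, need a low total or an event already noticed, so the isolated, silent case remains uncovered.

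The rates may also be too high for this trial. Table 1 describes renal transplant patients, and section 6.4 says: "Most of these side-effects were reported in patients who used sirolimus in combination with other immunosuppressive drugs". Patients on other immunosuppressive therapy are excluded here, and the protocol expects that side-effects might be less frequent. This stands too. A reader might take 4.9% to 41% as the chance of missing a case. It is the chance of any case at borrowed rates, and cases that lower the total would be flagged as leukopenia.

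Finally, the plan never promises a test for every entry in Table 1, and a table of total leukocytes makes no claim about neutrophils. That is fair: there is no direct contradiction, and misreading the summary is a risk rather than a certainty. But section 11.2 does rely on laboratory testing for early detection, and for isolated neutropenia the scheduled tests cannot provide it.

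**Conclusion.** The gap is real but narrow. At the scheduled visits, the plan as written would not detect neutropenia that is isolated, without symptoms and accompanied by a total leukocyte count of at least 4.0 x10E9/L. Other forms could still be found through the leukocyte limit or adverse event follow-up.

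The chance of any neutropenia among 5 patients is 4.9% to just under 41% if Table 1's band applies and patients are independent. The share that would be missed is smaller by an unknown amount, and the documents give no rate for patients with FAP. No planned analysis depends on the neutrophil count. This is an inexpensive improvement to the safety outcome, not a flaw that undermines the study.

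**What to change.** In footnote 1 of section 3 and in the laboratory list of section 7.2, replace leukocytes by leukocytes with automated differential at baseline, month 3 and month 6. Report neutrophil counts descriptively by visit in the laboratory summary. The baseline count has to be specified before enrolment, because each patient's later values are read against it.

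The differential uses blood already drawn (up to 15 samples, 10 of them on treatment), with no extra visit or procedure. The downside is a small laboratory cost and a few more flagged values.

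If the panel is left as it is, the safety results should state that neutropenia was not assessed by the scheduled panel, so that its absence from the tables is not read as absence of the event. No change to any withdrawal or treatment rule is proposed.
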